If any new information becomes available during the course of the study that may affect the patient's willingness to participate in the study, they should be given a new and updated informed consent form so they can give their consent to their continued participation.

XIV.2 - ACCESS TO SOURCE DATA

The investigator must provide the CRA with direct access to any source documents relating to the patient that may be required to verify the data recorded in the case report form.

With regard to electronic patient records, if they do not come from validated software with an audit trail and if access cannot be limited to the patients in the study, the investigator must provide a signed hard copy of the electronic medical records during the CRA's visits.

If so requested by the relevant authorities, the investigator must provide access to all study data.

In accordance with the regulations and CBP recommendations, the patient will be informed in writing of the need to verify their data in the medical file for quality control, audit or inspection.

XIV.3 - CONDUCT OF THE STUDY

The study will be conducted in accordance with Clinical Best Practices (CBP), the Declaration of Helsinki and applicable European and/or local laws and regulations related to the proper conduct of clinical studies.

XIV.4 - ETHICS COMMITTEE AND RELEVANT AUTHORITY

The sponsor will submit this Protocol along with the other essential study documents to the CPP. Before starting the study, the investigator should have received a positive recommendation from the CPP for the Protocol and the patient informed consent form. This positive recommendation from the CPP will be forwarded to the ANSM as soon as it has been received.

The CPP and the ANSM will be informed of the implementation and completion of the study.

During the course of the study, the sponsor must inform the CPP of any changes to the Protocol and/or essential documents (see section XIV.6).

Medical device vigilance cases will be reported to the relevant authorities (see section VIII).

XIV.5 - SPECIFIC NATIONAL PROCEDURES

XIV.5.1 - COMMISSION NATIONALE DE L'INFORMATIQUE ET DES LIBERTES [FRENCH DATA PROTECTION AUTHORITY] (CNIL)

In accordance with the current version of the French Law 78-17 called "Informatique et Libertés" of 6 January 1978 and Regulation (EU) 2016/679 of the European Parliament and of the Council of 27 April 2016 on the protection of natural persons with regard to the processing of personal data and on the free movement of such data (General Data Protection Regulation - GDPR), the sponsor has undertaken to comply with the CNIL's MR-001 Reference Methodology.

Patients will be informed that their personal data, collected as part of the study, will be kept confidential and will be processed electronically in countries inside or outside the European Union under the responsibility of the sponsor. They will also be informed of their rights regarding the processing of their data. They will be given an information leaflet and an informed consent form that must be signed prior to any study procedure taking place.

XIV.5.2 - CONSEIL NATIONAL DE L'ORDRE DES MEDECINS [FRENCH NATIONAL MEDICAL COUNCIL] (CNOM)

In accordance with article R1121-3-1 of the French Public Health Code, a tripartite financial agreement, called the "Convention Unique", will be signed by the sponsor, the healthcare facility, the investigator and the PSAD, and will be sent to the CNOM for information purposes.

In accordance with French Act No. 2011-2012 of 29 December 2011 and its implementing Decree No. 2013-414 of 21 May 2013 relating to the transparency of potential conflict of interests, the sponsor will publish the existence of this agreement as well as the benefits, in cash or in kind, provided directly or indirectly to the investigator.

XIV. 6 - AMENDMENTS

Neither the investigator nor the sponsor may amend the Protocol without the consent of the other party. Any amendments that are likely to be issued must be dated and signed by both parties and must appear as amendments to the Protocol before implementation.

Substantial amendments must be submitted to the CPP for its opinion before the changes are implemented. The positive recommendation(s) obtained will be sent to the ANSM for information purposes.

A substantial amendment is an amendment that has a significant impact on the safety integrity of the study's patients, the scientific value or conduct of the study, or the quality or safety of the medical device.

Substantial amendments pertaining to safety measures will be submitted to the CPP for its opinion but may be implemented immediately under specific conditions defined by the sponsor.

Non-substantial amendments are not submitted to the CPP, but the related changes, whose documentation is kept by the sponsor are highlighted upon submission of any subsequent substantial amendments.

XIV. 7 - AUDIT AND INSPECTION

The investigator must consent to making the study source documents available to the auditors (qualified personnel of the sponsor or its representative) or health authority inspectors. The investigator will make themselves available to answer any questions raised by the auditors/inspectors and will do everything possible to facilitate the audit/inspection process.

In the event of an inspection, the investigator may inform the sponsor.

XV - PUBLICATION OF DATA

All data and results from the study are the exclusive property of the sponsor. They must be neither communicated nor published without the prior authorisation of the sponsor.

The sponsor reserves the right to publish or use them in any form whatsoever, to submit them for registration to the health authorities of any country, on its own behalf or on behalf of its subsidiaries.

The investigators should inform the sponsor of any plans to publish or present the study data. Any publication or presentation of the results (abstracts in scientific journals or reviews, oral presentations, etc.), in whole or in part, by the investigators or their representatives should be reviewed by the sponsor before submission.

In the event that the study generates patentable results, the sponsor will be authorised to file such a patent, on their own behalf and at their own expense.

The final clinical study report will be prepared in accordance with applicable regulations.

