- The reference of the study equipment (MDs, consumables and/or replacement equipment) that was destroyed/recycled (batch number).
- Quantity destroyed/recycled.
- Date and method of destruction/recycling.
- Name and signature of the individual (or company) responsible for destroying/recycling the study equipment.

Batch reconciliation and destruction/recycling certificates will be kept in the PSAD's study file, the Investigator Site File (ISF) and the sponsor's Trial Master File (TMF).

At the end of the study, for each of the patients involved, the sponsor undertakes to take all possible measures towards ensuring continuity of the care chain.

V.3 - DURATION OF TREATMENT

The "closed-loop" automated insulin delivery system (or "artificial pancreas") will be used according to the instructions provided in the user manual and summarised above, during the 3-month follow-up period, unless the study is terminated early (see section IV.3).

V.4 - ADHERENCE/COMPLIANCE

Patient adherence and compliance are assessed using the "Patient acquired knowledge assessment" questionnaire (see section VI.10.5), completed by the PSAD nurse, at each visit/interaction during the patient's follow-up period, by asking the patient about their use of the "closed-loop" automated insulin delivery system (or "artificial pancreas"), including regular physical activity and meals.

The time spent in a "closed loop", which the investigator gathers via the data visualisation platform, also documents patient adherence and compliance.

V.5 - CONCOMITANT TREATMENTS / FIRST AID KIT / CONTRAINDICATIONS

V.5.1 - CONCOMITANT TREATMENTS

Since the purpose of this study is to assess PSAD support for patients equipped with an automated "closed loop" insulin delivery system (or "artificial pancreas"), and not to assess the effectiveness of the system itself, it is the clinical investigators' responsibility to establish the treatment(s) required for proper patient management in accordance with the rules of clinical best practices and the recommendations described in the user manual. Please note: treatments that could affect the physiology of diabetes, i.e. that lead to interactions with blood sugar and/or insulin and are thus liable to interfere with the action of "closed-loop" automated insulin delivery systems (or "artificial pancreas"), are not authorised for use in patients equipped with these systems (e.g. steroid treatment).

V.5.2 - FIRST AID KIT

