- The collection of any adverse events / SAEs / incidents. If an adverse event is reported, the PSAD nurse passes the information on to the investigator for patient assessment and monitoring if necessary

At the end of the interview, the PSAD nurse reminds the patient to complete the J30 patient booklet and return it in the pre-paid envelope they were given during their hospital stay or hand it to the investigator if the 1-month follow-up takes place during a hospital visit. They record this visit in the PSAD files and complete the e-CRF. They send a written report to the investigator with their assessment of the patient's training and the list of adverse events (where applicable).

At the end of their interview with the PSAD nurse, the patient completes the D30 patient booklet, which consists of the following questionnaires:

- You and the "closed-loop" automated insulin delivery system (or "artificial pancreas") (Perceived benefits)
- You and your quality of life with diabetes (EQ-5D-5L)
- You and your beliefs about the medical treatment (BMQ – specific section only)
- You and your daily constraints
- You and your management in general (CSQ-8: Overall satisfaction)
- You and your management by your home healthcare provider (Proactiveness / availability / PSAD nurse advice)
- You and your quality of life and daily constraints linked to the risk of hypoglycaemic episodes (HFS-II)

The patient sends the completed D30 patient booklet to the investigator as soon as possible using a pre-paid envelope provided to the patient or gives it to the investigator if the 1-month follow-up takes place during a hospital visit. Once received, patient questionnaires will be entered in the e-CRF by the investigator or a member of the hospital team delegated by the investigator and filed in the patient's source file.

VI.7.2 - FOLLOW-UP ON D30 BY THE INVESTIGATOR

This follow-up can be performed during a hospital visit or by remote consultation at the investigator's discretion. The investigator will retrieve data on the patient's metabolic balance over the last 4 weeks from the data visualisation platform:

- Daily average blood sugar level and its variability (standard deviation and coefficient of variation, if applicable)
- Time spent (as a percentage):
 - In hyperglycaemia (> 180 mg/dl), [180-250 mg/dl] and > 250 mg/dl
 - In the blood sugar target [70-180 mg/dl]
 - In hypoglycaemia (< 70 mg/dl), [54-70 mg/dl] and < 54 mg/dl
- % of time spent in closed loop (if available)

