- The D30 patient booklet, including the following questionnaires if follow-up takes place in the hospital:
 - You and the "closed-loop" automated insulin delivery system (or "artificial pancreas") (Perceived benefits)
 - You and your quality of life with diabetes (EQ-5D-5L)
 - You and your beliefs about the medical treatment (BMQ – specific section only)
 - You and your daily constraints
 - You and your management in general (CSQ-8: Overall satisfaction)
 - You and your management by your home healthcare provider (Proactiveness / availability / PSAD nurse advice)
 - You and your quality of life and daily constraints linked to the risk of hypoglycaemic episodes (HFS-II)

The investigator ensures that the patient meets the criteria for continued use of the system (patient follows the technique; sufficient use of the [REDACTED] "closed-loop" systems [REDACTED] [REDACTED] (minimum use time 75% for semi-closed-loop) and regular observation of results in real-time) and does not present any discontinuation criteria (choice of the patient and/or their family; poor tolerance; use time for the closed-loop system less than 75%; failure to comply with the follow-up consultation instructions; misuse of or damage to the equipment). If necessary, use of the system must be discontinued and the reasons for the discontinuation given.

VI.8 - VISIT ON D90 BY THE PSAD NURSE (D90 ± 15 DAYS)

This visit, three months after the "closed-loop" automated insulin delivery system (or "artificial pancreas") is installed, will be carried out by the PSAD nurse at the patient's home. It should be used to assess the patient's knowledge (continuous technical training and reminder of the initial technical training) and confirm their best practices. This visit should be carried out before the patient's end-of-study visit at the centre.

Remote technical monitoring takes place throughout the follow-up period. The PSAD nurse views the patient's data on the platform of the "closed-loop" automated insulin delivery system (or "artificial pancreas") to detect any technical problems and checks the technical data is transmitted correctly.

The interview includes:

- An assessment of the patient's knowledge at both the beginning and end of the training and the patient acquired knowledge assessment questionnaire, completed by the PSAD nurse in the e-CRF.
- A point-by-point review of the initial technical training by having the patient repeat the necessary operations.

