The number of patients is small and the proportion of expected missing or invalid data is small and randomly distributed. Consequently, no imputation procedure for missing or invalid data will be applied. If necessary, the replacement of some of these data will be detailed in the SAP on a case-by-case basis.

X.3.2 - AVAILABILITY OF THE PATIENTS

The number of patients included, fitted with the device, prematurely discharged before being fitted and prematurely discharged after being fitted will be described. The reasons for early discharge will also be described.

The analysis populations and number of patients per sub-group will also be described.

X.3.3 - DEMOGRAPHICS AND INCLUSION CHARACTERISTICS

Descriptive statistics (number, mean, standard deviation, median, Q1, Q3, minimum and maximum) will be used to present the inclusion characteristics and demographic data of intent-to-treat patients.

X.3.4 - ANALYSIS OF THE PRIMARY ASSESSMENT CRITERION

To meet the main objective, the overall CSQ-8 score will be calculated at each time of assessment. The percentage of patients satisfied on D30 and D90 and the percentage of patients with continued satisfaction on D90 will be described. The 95% CIs will also be presented.

The absolute variation of the overall CSQ-8 score and the relative variation in relation to D30 will also be described on D90.

Each item of the questionnaire "You and your management by your service provider" will be described at each time of assessment. Scores based on the scales from 1 to 10 will be presented using descriptive statistics.

X.3.5 - ANALYSIS OF SECONDARY ASSESSMENT CRITERIA

Home healthcare provider (PSAD) management

Management description

For each phase of the study (pre-installation, installation and follow-up), the number of interactions will be described. The type of interaction (visits/telephone calls), the time spent per interaction, the main reason and secondary reason for making contact will also be presented.

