For each item in the "You and your daily constraints" questionnaire, the percentage of patients with this constraint will be described at inclusion, on D30 and D90. The number of constraints ticked by the patient will also be presented.

The total HFS-II score and the scores from the two sub-categories, “HFS-B” and “HFS-W”, will be presented at inclusion, on D30 and on D90, along with the absolute and relative variations on D30 and D90 compared with the time of inclusion.

Expected and perceived benefits

For each item in the "You and the "closed-loop" automated insulin delivery system (or "artificial pancreas")" questionnaire, the percentage of patients who answered "Yes, I hope so" or "I don't have any expectations regarding this matter" will be described at inclusion. The confidence level score for the technical use of the system will also be prepared.

On D30 and D90, for each item of the questionnaire, the percentage of patients who answered "Yes, I perceived benefits" or "I didn't perceive any benefits" will be described. The confidence level score on D30 and D90, as well as the absolute and relative variation compared to the time of inclusion will also be described.

Beliefs about the medical treatment

For each BMQ-specific question, the percentage of patients who answered: strongly disagree / disagree / uncertain / agree / strongly agree will be described.

The BMQ-specific score related to the need for the treatment and the score relating to concerns will be described at inclusion, on D30 and D90. The absolute and relative variations in these two scores compared to the time of inclusion will be calculated on D30 and D90.

Investigator questionnaire

Responses to all items in the investigator questionnaire will be described for the investigator population. The answers to text entry fields will be presented in a list.

Clinical course

The average HbA1C value will be described at installation and on D90. The percentage of patients with an HbA1C < 7% will also be calculated at installation and on D90.

The parameters below will be presented using descriptive statistics:

- Percentage of time spent over a 4-week period (if available) in the blood sugar target, hypoglycaemia and hyperglycaemia, at inclusion, on D30 and on D90.
- Percentage of time spent using a closed-loop system over a 4-week period (if available) on D30 and D90.

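### Low closed-loop use on D30 is a criterion for stopping the system, so missing D90 closed-loop time can depend on the D30 value; the plan treats it as random and may overstate sustained use

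*Combined protocol and SAP*

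**What the plan says.** **Role of the variable.** V.4 of the protocol assesses adherence first through the acquired-knowledge questionnaire. It adds that closed-loop time, read from the data platform, "also documents patient adherence and compliance". VI.10.3 adds the consumption of consumables.

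**D30 check.** Under VI.7.2 the investigator retrieves 4-week glucose data and the percentage "of time spent in closed loop (if available"), then checks criteria for continuing and for stopping the system. The continuing criteria include "minimum use time 75% for semi-closed-loop". The stopping criteria include "use time for the closed-loop system less than 75" per cent. The section closes: "If necessary, use of the system must be discontinued and the reasons for the discontinuation given".

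**Analysis.** X.3.5 (Clinical course) plans descriptive statistics for "Percentage of time spent using a closed-loop system over a 4-week period (if available) on D30 and D90" and for "Percentage of time spent over a 4-week period (if available) in the blood sugar target, hypoglycaemia and hyperglycaemia, at inclusion, on D30 and on D90", and describes HbA1c at installation and on D90. X.3.1 imputes nothing, on the ground that "the proportion of expected missing or invalid data is small and randomly distributed". The intent-to-treat set in X.2.1 is every fitted, eligible patient, with no condition on D30 use. X.3.2 counts premature discharges from the study after fitting and gives their reasons. Nothing in X.3 reports stops of the system.

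**Early leavers.** VI.9 foresees an end-of-study visit for every patient. An early-discharge visit has the same procedures, closed-loop time included, where feasible. The schedule in VI.1 puts D90 and early withdrawal in one column.

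**The concern.** The same variable documents adherence and helps decide who can supply its next value. If a patient is taken off the system because D30 use was low, and D90 closed-loop time is then treated as unavailable, the D90 summary loses low users. A D30 summary set beside a D90 summary could show a rise although nobody used the system more. Readers could take that as adherence sustained under home-provider support.

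The plan leaves several things unstated:
- whether stopping the system means leaving the study;
- whether a stopped patient's D90 closed-loop time is zero, missing, or the last 4 weeks on the system;
- whether early-discharge values enter the D90 summary;
- whether D90 glucose and HbA1c from a patient off the system, if assessed, are pooled with on-system values.

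**Working it through.** **The plan's own figure.** The documents give no expected distribution of closed-loop use. The only precision figure is in X.1 and concerns satisfaction: 1.96 × √(0.85 × 0.15 / 32) = 12.37%, which agrees with the stated bound of 12.4%. Only n = 32 is carried over from it.

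**Step 1: the missingness premise.** X.3.1 needs absence of a value to be unrelated to the value. VI.7.2 allows absence on D90 to follow from a low value on D30. Where that criterion is acted on, the two statements cannot both hold for closed-loop time.

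**Step 2: size of an artefactual rise.** Assumptions, none from the documents: k of 32 patients use the system 60% of the time, the rest 90%; nobody's behaviour changes; the k patients are stopped and have no D90 value.
- D30 mean = [(32 − k) × 90 + k × 60] / 32
- D90 available-case mean = 90
- Apparent rise = 90 − D30 mean = 30k / 32
- D90 mean over all fitted patients, 0% when off the system = (32 − k) × 90 / 32

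| k stopped | D30 mean | D90 available-case | Apparent rise | D90 all fitted, off = 0% |
|---|---|---|---|---|
| 1 | 89.1% | 90% | 0.9 points | 87.2% |
| 3 | 87.2% | 90% | 2.8 points | 81.6% |
| 5 | 85.3% | 90% | 4.7 points | 75.9% |

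The last column answers a different question, use among everyone fitted with a stop counted as no use. Its gap to 90% does not measure the artefact.

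**Step 3: sensitivity.** D30 and D90 use were simulated as correlated normal variables limited to 0–100, with correlation 0.5 or 0.8 and with 50% or 100% of patients below 75% on D30 stopped. All these values are assumptions.

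| Assumed mean / SD | Below 75% on D30 | Available-case D90 mean minus mean if all continued | Available-case D90 mean minus mean with stopped = 0% |
|---|---|---|---|
| 90 / 8 | 3% | 0.1 to 0.5 points | 1.3 to 2.8 points |
| 85 / 12 | 20% | 0.9 to 3.2 points | about 9 to 18 points |
| 80 / 15 | 37% | 1.6 to 6.8 points | about 15 to 32 points |

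**Step 4: the early-discharge visit.** In Step 2 with k = 3, entering 60% for the stopped patients gives (29 × 90 + 3 × 60) / 32 = 87.2% on D90, so the rise vanishes. In Step 3, with the D30 value standing in for the early-discharge value, the D90 mean lies 0 to 2.8 points below the all-continue mean. The reported figure therefore turns on a handling rule that the plan does not give.

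**The case against.** The case on the other side has several parts.

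- **Stopping is discretionary.** The closing sentence of VI.7.2 is conditional, so a patient below 75% may continue. This stands. Selection may be partial or absent, but where it occurs it acts on the outcome and goes unreported.
- **Early leavers are assessed.** VI.9 provides the visit and extends the continued-use assessment to patients discharged prematurely. This also stands and may remove the overstatement. However, the procedures are done only where feasible, and no rule says whether the values count as D90 values. For a patient stopped near D30, the last 4 weeks would largely repeat the D30 window.
- **Reasons are partly covered.** IV.3 has investigator's decision and other as reasons for leaving, and X.3.2 reports discharges with reasons. V.3 suggests that stopping may mean leaving. None of this identifies stops for low use, and the reasons required by VI.7.2 have no planned table.
- **Handling is deferred.** IX.2 leaves missing data to the pre-lock review, and X.3.1 allows case-by-case replacement in an SAP still to be drafted. That gives room to fix the point but does not repair the stated premise.
- **The stakes are modest.** Closed-loop time is one of several adherence sources, X.3.5 plans no D30-to-D90 change for it, and V.5.1 says that the study does not assess the system's effectiveness. This stands and limits the weight of the point.

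A reader might infer that the D90 distribution is truncated at 75%, or that D90 glucose describes mainly patients who passed the cut-off. The documents support neither: stopping is not automatic, the share below 75% is not given, and no relation between use and glucose is quantified.

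**Conclusion.** The point holds in a limited form. A discretionary stopping criterion based on closed-loop use makes it possible for missing D90 closed-loop time to depend on D30 use. That contradicts the premise on which X.3.1 rests its handling of missing data. The available-case description in X.3.5 may then overstate sustained use. A certain overstatement is not shown.

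The size cannot be fixed from the documents. With the assumed 90% and 60% use it is 0.9 to 4.7 points for 1 to 5 patients stopped. Across the simulated scenarios it is 0.1 to 6.8 points against everyone continuing, and it disappears on that comparison if early-discharge values are entered as end-of-study values. The primary satisfaction criterion is not the subject of this point.

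The two 75% wordings in VI.7.2, one for semi-closed-loop and one for closed-loop, might be read as contradictory. They sit beside redacted text, so no contradiction can be asserted.

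**What to change.** Analysis only, in X.3.2 and X.3.5 or the SAP:

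1. Report the number and percentage of fitted patients whose system was stopped, by the reasons already recorded under VI.7.2, with use below 75% as its own category.
2. Describe D90 closed-loop time for patients still on the system and, beside it, for all fitted patients with 0% when off the system, labelled as such.
3. Keep early-discharge values separate from D90 values.
4. Where patients off the system are assessed on D90, show glucose metrics and HbA1c by on/off status.
5. Remove the statement that missing data are randomly distributed for these variables.

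The cost is some SAP wording, one extra table and a possibly less favourable D90 use figure. X.3 has the SAP drafted before the database is frozen, so there is time.

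On the care rule, the only request is that the sponsor reconcile the 75% criterion in VI.7.2 with the availability proviso attached to the same measure in that section.
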